**B. Sample Size and Enrollment:**

One hundred twenty (120) participants, 50 at UTHSCSA site, and 35 each at The University of Louisville Research Foundation, Inc. and The University of Cincinnati, will be involved in the clinical trial in Aim 2. All study participants will sign informed consent forms prior to being enrolled and will be recruited from the UTHSCSA, the University of Louisville or the University of Cincinnati.

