**Inclusion Criteria:**

1. Male or female outpatients 18 years of age or older
2. Bipolar I or II disorder as assessed by MINI 6.0
3. In psychiatric outpatient treatment at UTHSCSA, University of Louisville, or Lindner Center of Hope, Mason Ohio
4. Currently taking mood stabilizer or second generation antipsychotic for 4 weeks or longer
5. Ability to access Kios-Bipolar or eMoods (via computer, smartphone or tablet)

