**Table 2. BISS Item and Corresponding KIOS-BIPOLAR Questionnaire**

BISS Item	KIOS-BIPOLAR Question
Affective Lability	Have your emotions shifted fairly suddenly at times?
Sadness	Have you felt depressed, sad or down?
Irritability	Have you felt easily irritated, angry or resentful?
Pessimism	Have you been discouraged, pessimistic or felt hopeless?
Anxiousness	Have you felt tense or anxious?
Less Need for Sleep	Were there nights you needed less sleep than usual?
Psychomotor Slowing	Have you felt slowed down?
Energetic	Have you had more energy than usual to do things?

**Software:** Subjects assigned to KIOS-Bipolar will have the app loaded onto their preferred device. The program is available for iPhone and Android devices, and accessible on a pc. The research coordinator will demonstrate the KIOS-Bipolar operation with the subject and ask the subject if he/she has any questions about the procedures of the trial. A phone number and email address will be provided to allow the subject to make contact if any question arises after leaving the clinic. The data entry procedure will take less than 5 minutes per session, with most subjects completing their entries in 2 minutes.

For participants who have been randomized to the eMoods App an additional procedure will occur. After each completed weekly entry on eMoods, the participant will have the option to email the results to the Research Coordinator weekly or postpone sending data until their scheduled research visit.

The subject will be told that an email, text, or push notification reminder will be sent one day after a missed scheduled assessment. The participants phone number will be shared with a third-party (Twilio) solely for the purpose of reminding the participant to complete their questionnaire. This information will only be used for the administration of the push notification and will be kept strictly confidential. The participant will not have the option to opt out of the notification. For participants randomized to KIOS-Bipolar, a text message reminder will be sent one day after a missed scheduled assessment. The participant's phone number will be added to New Patient section in KIOS-Bipolar.

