It should be noted that the Summary Statement contained a criticism that email reminders prior to expected assessment days would be a direct intervention that confounds weekly reporting adherence. Because the reminder will be sent *after* the scheduled assessment day, we are still able to judge adherence to the study schedule; the response to the notifications will provide a relevant secondary outcome measure. In addition, many subjects in the Field Trial requested this feature, which will almost certainly be included as an option in the commercialized version of KIOS-Bipolar.

Study participants assigned to eMoods will also have the software downloaded on their device (Either Android phone or computer) and the procedure of demonstrating the software and providing contact information described above will be followed. In the case that the IOS version of eMoods is not available by the time the study begins, the randomization of subjects will be stratified by device to ensure equal representation in the treatment groups.

Participation in the study will not impact the patient's routine clinical care for his/her bipolar condition. However, some subjects may want to discuss their KIOS-Bipolar or eMoods experience with their psychiatrist and/or psychologist, and will be permitted to do so.

Participants randomized to their assigned group who are unable to complete their weekly entries based on the following criteria: technical difficulties completing the weekly entry, difficulty emailing data to Research Coordinator (for eMoods group), and any other technical issues that may arise throughout the course of the study will have the option to switch to the other group. The participants who have been switched to the other group will have to complete a BISS self-report form along with a weekly entry from the newly assigned group.

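### Eligibility can be met with access to only one app, so if eMoods has no iOS version, people with only an iPhone or iPad can be randomised to an app they cannot run, and stratifying by device does not prevent it

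*Combined protocol and SAP*

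**What the plan says.** Inclusion criterion 5 reads "Ability to access Kios-Bipolar or eMoods (via computer, smartphone or tablet". No other part of the protocol requires access to both tools.

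The two tools do not cover the same devices. The Software text after Table 2 says of KIOS-Bipolar: "The program is available for iPhone and Android devices, and accessible on a pc". For eMoods the device given is "Either Android phone or computer".

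The protocol foresees a gap for Apple devices and deals with it conditionally: "In the case that the IOS version of eMoods is not available by the time the study begins", then "the randomization of subjects will be stratified by device to ensure equal representation in the treatment groups". It adds no restriction on who may enter or on which arm they may be assigned to.

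Later in the same text, participants who cannot complete weekly entries for technical reasons "will have the option to switch to the other group". The listed reasons include one that belongs to a single arm, "difficulty emailing data to Research Coordinator (for eMoods group". The Plan of analysis does not say in which group a person who switches is counted.

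**The concern.** Stratification deals with imbalance between arms, whereas the problem here is access. Spreading people who own only an iPhone or iPad evenly over the two arms means that some of them are assigned to eMoods. If eMoods has no iOS version and they have no usable computer, they cannot use the tool they were assigned.

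This bears on the outcomes the plan puts first. The Plan of analysis names adherence and attrition as its primary aims. Hypotheses b and c state that persistence and on-time completion will not differ between the arms. An app that cannot be opened produces missed weeks that say nothing about willingness to use it.

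If the affected people switch instead, the comparisons in hypotheses a and e (time in remission, time in syndromal states, LFQ) are diluted when analysed as randomised. Analysed by the app actually used, they are confounded with device ownership. For the hypotheses of no difference, dilution also favours the predicted result.

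**Working it through.** **Step 1. Who is exposed.** Setting the device lists side by side:

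- KIOS-Bipolar: iPhone, Android, PC (Software).
- eMoods: Android phone, computer; iOS uncertain at study start (Software).
- Eligibility: either tool, by computer, smartphone or tablet (criterion 5).

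Every platform listed for eMoods is also listed for KIOS-Bipolar, but not the reverse. A person with an iPhone and a computer can run both. The exposed group is therefore people with only an iPhone or iPad and no usable computer, and only if the iOS version is missing. For them, a switch caused by device incompatibility can run only from eMoods to KIOS-Bipolar.

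**Step 2. The plan's own figure.** The Plan of analysis claims power 0.80 for 0.65 against 0.5 with n = 90, two-sided 0.05. With the continuity-corrected normal formula:

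- SE under 0.5 = √(0.25/90) = 0.0527; SE under 0.65 = √(0.65 × 0.35/90) = 0.0503.
- Power = Φ[(0.15 − 1/180 − 1.96 × 0.0527)/0.0503] = Φ(0.82) = 0.79. The exact binomial gives 0.81.

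The figure reproduces, but it is a one-sample calculation. The plan gives no power for comparing the arms, so what follows is illustration and corrects no stated number.

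**Step 3. Affected people stay in eMoods.** Inputs: the total from section B, "One hundred twenty (120) participants, 50 at UTHSCSA site, and 35 each", split 1:1 (the ratio is not stated; assumed), so 60 per arm; true persistence 0.80 in both arms (assumed); a share s of the eMoods arm who cannot run it and do not persist (assumed). Observed eMoods persistence is then 0.80 × (1 − s), and the artificial difference is d = 0.80 × s. With p̄ the mean of the two proportions,

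- SE0 = √[2p̄(1 − p̄)/60]
- SE1 = √[0.80 × 0.20/60 + p₂(1 − p₂)/60], where p₂ = 0.80(1 − s)
- Probability of a significant result favouring KIOS-Bipolar = Φ[(d − 1.96 × SE0)/SE1]

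| s | People | p₂ | d | SE0 | SE1 | z | Probability |
|---|---|---|---|---|---|---|---|
| 5% | 3 | 0.76 | 0.04 | 0.0756 | 0.0755 | −1.43 | 0.08 |
| 10% | 6 | 0.72 | 0.08 | 0.0780 | 0.0776 | −0.94 | 0.17 |
| 20% | 12 | 0.64 | 0.16 | 0.0820 | 0.0807 | −0.01 | 0.50 |
| 30% | 18 | 0.56 | 0.24 | 0.0852 | 0.0823 | 0.89 | 0.81 |

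With nobody affected, the probability in this direction would be 0.025.

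**Step 4. Affected people switch.** If they all move to KIOS-Bipolar and respond as that arm does, a true difference D becomes D × (1 − s) as randomised, a loss of 10%, 20% or 30%. The sample needed for the same power rises by about 1/(1 − s)², that is 1.23, 1.56 or 2.04 times. Groups formed by the app used would be 66 and 54, 72 and 48, or 78 and 42, and would no longer be the randomised groups.

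**The case against.** Several points on the other side have force.

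- **The gap is conditional.** A reader might infer that the iOS version of eMoods is missing. The documents do not say so; they provide for the case. If it was available at the start, the device problem largely disappears. The contingency is nevertheless the protocol's own, and the device list for eMoods still names only Android phone or computer.
- **Not every iPhone owner is affected.** A computer is a permitted route for eMoods, so the exposed group is smaller than all Apple users and may be very small. At 5% the distortion in Step 3 is modest.
- **Criterion 5 may mean the assigned tool.** The protocol elsewhere names the two tools together in that sense. But eligibility is settled before assignment, so on that reading too the criterion checks nothing unless access to both is confirmed.
- **Other safeguards exist.** Exclusion criterion 1 removes people unable to comply, and staff install and demonstrate the app. The exclusion does not mention devices, and the demonstration is described for people already assigned, so neither clearly acts before randomisation.
- **Switching is two-way.** A reader might infer that crossover as a whole runs in one direction. The rule as written is open to both arms and covers any technical problem, and KIOS-Bipolar software is itself being refined during the trial. Only incompatibility-driven switches are one-way, though the emailing reason also applies to the eMoods arm alone.
- **No definite loss of power can be claimed.** With an effect chosen to give 80% power at 60 per arm (0.745 against 0.50), switching by 10%, 20% or 30% would lower power to 0.71, 0.62 or 0.51. The plan states no such effect, and switching is optional, so these figures do not measure this trial.

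**Conclusion.** The point stands in conditional form. As written, eligibility does not ensure that a participant can run the app they are assigned. If eMoods has no iOS version at study start, stratifying by device leaves that gap open for people with only an iPhone or iPad and no usable computer. The result would be either lower eMoods adherence through lack of availability, or device-driven moves from eMoods to KIOS-Bipolar with no stated rule for analysing them.

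The size cannot be fixed from the documents, because they do not give the affected share. The illustrative probabilities rest on 1:1 allocation, true persistence of 0.80 in both arms, and affected people staying in eMoods without persisting. The proportional shrinkage rests on all of them switching. A mixture of the two would distort both adherence and outcome comparisons, each to a lesser extent.

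**What to change.** 1. Reword inclusion criterion 5 to require that the participant can access both KIOS-Bipolar and eMoods on a device they use, and check this before randomisation.
2. If randomisation is stratified by device, keep device as a stratum and include it as a term in the analysis. It serves balance and precision and does not replace the access check.
3. Record the reason for and direction of every switch. The new criterion removes device incompatibility, but switches for other technical reasons will remain.
4. State in the Plan of analysis that the main comparison is by randomised group, with any analysis by app used labelled as supportive.

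The cost is an amendment to one criterion, a short device check at screening, a field on the case report form and a sentence or two in the analysis plan. The real trade-off is that people with only an iOS device are not enrolled until an iOS version of eMoods exists, so recruitment may be somewhat slower and the sample slightly narrower. The change needs to be in place before randomisation, since device-driven crossover cannot be undone afterwards.

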Assumptions needed for each analysis will be examined to assure they are reasonably well met and the conclusions are valid. End of study overall improvement or not for each measure can be analyzed with logistic regression using covariates and predictors of interest. By focusing analyses on proportions and changes in trajectories, each subject will serve as their own control and trends in improved scores, symptoms and behavior may be identified.

Initially, we will also assess the effects of site, ethnicity, and bipolar disorder subtype (BD I, BD II), but none of these factors will be retained in the final model if they are not shown to be significant moderating factors.

The rate of dropout at any given time will be modeled through logistic regression models, with health, socioeconomic, and treatment factors as explanatory variables. *The impact of quality of life on dropout will be assessed similarly.*

**Outcome Measures from KIOS Analytics:** Knowledge Base performance metrics will be computed to measure the effectiveness of the content provided to patients. These metrics take several forms and are based on changes in the symptom scores for all subjects in the field trial (see Phase I Final Report). Changes in the symptom scores provide a global measure of efficacy. Each of these measures can be computed as a function of changes, either over the course of the entire field trial or at each incremental assessment. This latter approach will provide a measure of effectiveness over time. Other KIOS analytic methods will reveal which specific content in the knowledge base needs improvement. Behavioral frequency analysis will show which patient states are entered most frequently. Behavioral transition analysis will show which conditions are precedents to undesirable states.

**Implementation of Clinical Trial Results into Final Product:** The results of the randomized trial will be used to make further refinements to KIOS-Bipolar. The KIOS-generated results will be used to guide changes to the knowledge base. Suggestions about additional features will be considered in development of the commercialization plans.

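### If randomisation is stratified by device, between-arm models should keep the stratum and results should be shown by device; a device covariate alone does not separate platform from app

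*Combined protocol and SAP*

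**What the plan says.** All references are to the combined protocol and SAP.

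**Randomisation.** The Software text in section D sets a condition, "In the case that the IOS version of eMoods is not available by the time the study begins", and then says that "the randomization of subjects will be stratified by device to ensure equal representation in the treatment groups". This is the only stratification factor in the document. The word device is not defined further.

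**Platforms.** The same text says of KIOS-Bipolar: "Subjects assigned to KIOS-Bipolar will have the app loaded onto their preferred device". It adds: "The program is available for iPhone and Android devices, and accessible on a pc". Participants assigned to eMoods "will also have the software downloaded on their device (Either Android phone or computer"). The fifth inclusion criterion asks only for "Ability to access Kios-Bipolar or eMoods (via computer, smartphone or tablet"), so it does not require a device that can run both apps.

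**Analysis.** The plan of analysis, under the heading on assessing KIOS-Bipolar or eMoods, names three factors: "we will also assess the effects of site, ethnicity, and bipolar disorder subtype (BD I, BD II"). Each is left out of the final model unless it proves to be a significant moderator. Logistic regression of end-of-study improvement may use covariates of interest, which are not listed. The dropout models use health, socioeconomic and treatment factors. Device is not mentioned, and no model comparing the two apps is written out.

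**The concern.** A factor used to balance the arms normally belongs in the analysis. Stratifying makes the arm difference less variable when the factor predicts outcome, and an unstratified standard error does not reflect that gain. Device could well predict weekly use of an app. Hypotheses b, c and d (persistence, on-time completion, satisfaction) all predict no difference and give no margin, so an interval that is too wide makes that prediction easier to declare met.

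The second issue has a different cause. In the very situation that triggers stratification, an iPhone owner assigned to KIOS-Bipolar can use the phone, while one assigned to eMoods needs a computer or an Android phone. If stratification balances the device owned, it does not balance the device used. A shortfall for eMoods in that stratum could reflect the app, the platform or both, and a single pooled figure would not show which. This would work in the opposite direction to the first issue, by producing a difference where the hypotheses expect none.

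**Working it through.** **The plan's own figures.** For 0.65 against 0.5 with n=90 at two-sided 0.05, the exact binomial power is 0.812 (stated 0.80). The two-group 95% half-width at n=30 and proportion 0.5 is 1.96 × √(2 × 0.25/30) = 0.253 (stated 0.25). At n=45 and proportion 0.9 it is 1.96 × √(2 × 0.09/45) = 0.124 (stated 0.12). The figure for n=40 comes to 0.219 at proportion 0.5, against a stated 0.20. None of these calculations uses device, and the one-sample figures cannot be affected by it.

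**Inputs.** The plan allows 30 of 120 to be lost, leaving 90. The rest are assumptions, because the documents do not give them: 1:1 allocation (45 per arm), the iPhone share, the outcome gap between device groups, a within-device SD of 0.25, and the penalty for entering data by computer instead of phone.

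**1. Standard error, per-subject on-time proportion.** With half the subjects in each device group, the ratio of the unstratified to the stratified standard error is √(1 + (gap/2)²/0.25²). The true error rate is 2 × [1 − Φ(1.96 × ratio)]. Power is from simulation (40,000 replicates) for a true difference of 0.15; with the stratum in the model it is about 0.80.

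| Device gap | SE ratio | True two-sided error | Power, stratum ignored |
|---|---|---|---|
| 0 | 1.00 | 0.050 | about 0.80 |
| 0.10 | √1.04 = 1.02 | 0.046 | 0.80 |
| 0.20 | √1.16 = 1.08 | 0.035 | 0.75 |
| 0.30 | √1.36 = 1.17 | 0.022 | 0.70 |

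**2. Standard error, yes/no outcome.** For a difference in proportions the ratio is √[p(1−p) / weighted mean of within-device p(1−p)]. Example: overall 0.8, half iPhone owners, device groups at 0.70 and 0.90. The within-device mean is (0.21 + 0.09)/2 = 0.15, so the ratio is √(0.16/0.15) = 1.033. The half-width is 1.96 × √(2 × 0.16/45) = 0.165 instead of 1.96 × √(2 × 0.15/45) = 0.160, and the true error rate is 0.043. Over iPhone shares of 30% to 60%, gaps of 0.1 to 0.3 and overall proportions of 0.5 and 0.8, the excess runs from 0.4% to 8%.

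**3. Platform.** Suppose the apps are identical and computer entry lowers the outcome for iPhone owners on eMoods. The false pooled difference is then iPhone share × penalty.

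| iPhone share | Penalty 0.10 | Penalty 0.20 | Penalty 0.30 |
|---|---|---|---|
| 30% | 0.03 | 0.06 | 0.09 |
| 50% | 0.05 | 0.10 | 0.15 |
| 60% | 0.06 | 0.12 | 0.18 |

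With 45 per arm and a base proportion of 0.8, the chance of a significant result runs from about 0.05 (share 30%, penalty 0.10) to 0.47 (60%, 0.30).

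**4. Does a device term remove it?** In a simulation of 200,000 runs (share 50%, penalty 0.2), the unadjusted and device-stratified differences were both 0.098, with rejection rates of 0.193 and 0.196. Within strata, the difference was 0.000 for Android and 0.200 for iPhone. Only the stratum-specific results show where the difference comes from.

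**5. Precision by stratum.** With 22 to 23 per arm and proportion 0.5, the half-width is 1.96 × √(0.5/22.5) = 0.29, against 1.96 × √(0.5/45) = 0.21 pooled. For a per-subject proportion with SD 0.25, the stratum half-width is 1.96 × 0.25 × √(2/22.5) = 0.15.

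**The case against.** Several points can fairly be made on the other side.

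- **The condition may never have arisen.** The documents do not say whether an iOS version of eMoods was available. This stands: the point is conditional. But the protocol wrote the contingency into the randomisation and did not carry it into the analysis.
- **The standard-error effect is conservative and may be small.** Gaps of 0.20 and 0.30 are 0.8 and 1.2 within-device SDs, and nothing in the documents supports gaps that large. At 0.10 the loss is negligible. This stands.
- **Much of the written plan is not a between-arm contrast.** The power figures are one-sample, subjects act as their own controls, and adherence is defined by KIOS-Bipolar entries. This also stands. The point bears on the between-group hypotheses, not on those figures.
- **Device could enter among the unlisted covariates.** It could, but nothing commits to it, and the one retention rule given would allow it to be dropped.
- **Device is undefined.** If it means the device used for entry, and that is balanced between arms, the platform problem largely disappears. The preferred-device wording leans towards ownership but does not settle it, which is itself a reason to define the stratum.
- **Platform availability may be part of the tool.** In a comparative effectiveness study that measures ease of use, this is a reasonable view. It is why the pooled comparison should stay as the main result, and why hypotheses b to d should not be moved to a single stratum, which would leave out randomised iPhone owners.

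A reader might infer that leaving device out of the model is what turns a platform difference into an apparent app difference. It is not. That difference comes from where each app runs, and step 4 shows that it is the same with device in the model.

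**Conclusion.** The point holds as two separate, conditional statements.

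First, if the stratified randomisation is used, between-arm analyses that ignore device overstate the standard error to the extent that device predicts outcome. The excess is 2% to 17% for a per-subject on-time proportion and 0.4% to 8% for a yes/no outcome, over assumed gaps of 0.10 to 0.30, and nil with no gap. The documents do not support an unqualified statement that the error bars are too wide or that power is lost.

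Second, a pooled difference can contain a platform component of up to iPhone share times the phone-computer gap, or 3 to 18 points over the assumed values. This is an upper bound. It takes every iPhone owner on KIOS-Bipolar to be using the phone, although a PC is allowed, and every iPhone owner on eMoods to bear the full penalty. Its likely direction is against eMoods. The documents do not establish that such a component will occur, only that the design as written permits it and the analysis as written would not reveal it.

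**What to change.** Add to the plan of analysis, to apply if randomisation is stratified by device:

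- The stratum is the device owned before randomisation, not the device later used.
- It is kept in every between-arm model whatever its p-value, and is exempt from the rule that drops non-significant factors.
- The pooled, stratum-adjusted comparison of the arms as randomised is the main result.
- For adherence, on-time completion, dropout and satisfaction, the arm difference is also reported by device stratum with its interval. The iPhone stratum is labelled app plus platform. The stratum where both apps run on the same type of device is labelled the like-for-like comparison.

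The cost is SAP wording and one or two degrees of freedom, depending on the number of device categories; no study procedure changes. The stratum-specific intervals will be wide (about ±0.29 for a difference in proportions with 22 to 23 per arm), so they should be read as description alongside the pooled result, not as separate tests.

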#### **ASSESS KIOS-BIPOLAR OR eMOODS:**

- a. At the beginning of the study subjects will be provided preformatted evaluation sheets and will be encouraged to note observations regarding ease/benefits of use, impediments to use, and suggestions for additional features that would enhance the utility of KIOS-Bipolar or eMoods for sustained health.
- b. We will ask the subjects to estimate how completing the KIOS-Bipolar /eMoods assessments contributed to their self-awareness, attitude, and overall sense of satisfaction with their health status.
- c. We will assess the sensitivity of KIOS-Bipolar to identify improving or worsening by comparing the concordance between subject-assessed items with staff -administered BISS items that address similar symptoms.

**Plan of analysis:** The primary aims of the analyses are to investigate patterns of adherence and attrition. The term adherence refers to the extent to which participants follow the weekly completion of KIOS-Bipolar's eight pivotal symptoms of bipolar disorder. Adherence will be measured through such usage indicators as the proportion of weeks completed on time, the proportion completed only with follow-up prompts, and the number of weeks not submitted. Proportions of stable trajectories or improving trajectories are of primary interest. With  $n=90$  subjects (which allows for as many as 30 of the enrolled 120 subjects to have met some criterion for early termination) in the study we will be able to estimate any proportion within 0.10 with 95% confidence. For proportions larger than 0.9 we will be 95% confident we are within 0.06 of the true proportion. For a trajectory neither improving nor degrading there should be a 0.5 proportion

UTHSCSA tracking number: HSC20150321H

of each. For any hypothesis test for a proportion improving or degrading, i.e. not 0.5, we have 0.80 power at two tail significance of 0.05 to detect 0.65 different from 0.5 with n=90 subjects. For subgroups of patients with n=45 we can detect 0.71 different from 0.5 and with n=30 we can detect 0.74 different from 0.5. When comparing proportions of two subgroups of subjects, we will be 95% confident that the difference in proportions of the two subgroups is less than 0.25 for subgroups of n=30 and smaller than 0.20 for subgroups of size 40. If the proportions are larger than 0.9 (i.e. less variable), then we will be 95% confident that the difference in proportions of two subgroups with n=30(45) is less than 0.15 (0.12).

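### Trouble emailing data lets eMoods participants cross to KIOS-Bipolar, although it is not inability to make the weekly entry, and this ground permits crossover in one direction only

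*Combined protocol and SAP*

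**What the plan says.** The relevant text is in the Software part of section D of the combined protocol and SAP, after Table 2.

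- **Extra step in one arm.** "For participants who have been randomized to the eMoods App an additional procedure will occur". Its place in the sequence is given as "After each completed weekly entry on eMoods", and its terms are that "the participant will have the option to email the results to the Research Coordinator weekly or postpone sending data until their scheduled research visit". No matching step is described for KIOS-Bipolar.
- **Switching rule.** It covers randomized participants "who are unable to complete their weekly entries based on the following criteria: technical difficulties completing the weekly entry", then adds "difficulty emailing data to Research Coordinator (for eMoods group), and any other technical issues that may arise throughout the course of the study". Such participants "will have the option to switch to the other group". A switcher completes a BISS self-report and goes on with weekly entries in the new app.
- **Outcomes exposed.** Under Plan of analysis, "The primary aims of the analyses are to investigate patterns of adherence and attrition", and one of the adherence indicators is "and the number of weeks not submitted". In section C, hypotheses a and e predict better clinical status and life functioning with KIOS-Bipolar. Hypotheses b, c and d predict no difference in persistence, on-time completion and satisfaction.

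The plan does not say how switchers are analysed, or whether an eMoods week that was entered but not sent counts as submitted.

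**The concern.** The switching rule has one condition, that the participant cannot make the weekly entry, and then lists reasons that are taken to meet it. Trouble with emailing does not fit. By the protocol's own sequence the entry is already complete when emailing begins, and sending need not happen that week.

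Only eMoods participants have the emailing step, so in a two-arm trial this ground can move people only towards KIOS-Bipolar. A person who can use the assigned app may therefore leave it because of a step in getting data to the study. What is at stake is the randomized clinical comparison, which such crossover weakens. The adherence and attrition results are also exposed, because the plan does not say how a switcher or an unsent week is counted.

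**Working it through.** **1. The two rules side by side.**

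| Question | Emailing step | Switching rule |
|---|---|---|
| When does it apply? | After a completed weekly entry | When the weekly entry cannot be made |
| Must it happen that week? | No, sending may wait for the visit | Not addressed |
| Which arm? | eMoods only | Both arms in general; emailing ground for eMoods only |

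A participant whose only problem is emailing has a completed entry and so does not meet the condition. If the condition governs, the emailing ground never operates. If the list governs, it is a one-way exit. The text does not settle which.

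**2. Plan figures.** The plan gives no switch rate and no calculation that allows for switching, so there is no figure of its own to reproduce on this point. Its power statement (0.80 for 0.65 against 0.5, n = 90) concerns a single proportion, not a comparison of arms. It is reproduced closely (exact binomial 0.812; normal approximation with continuity correction 0.793) and is not in dispute.

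**3. Clinical contrast, as randomized.**

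Inputs: 120 participants (section B); 60 per arm is assumed because no allocation ratio is stated; a share s of the eMoods arm switches on the emailing ground, s assumed.

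If switchers take on the full KIOS-Bipolar effect from the start, the eMoods arm mean is (1 − s) × μE + s × μK. The observed difference is then

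μK − [(1 − s) × μE + s × μK] = (1 − s) × (μK − μE).

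- s = 6/60 = 10%: 0.90 of the true difference remains. The sample needed for the same power rises by a factor of 1/0.90² = 1.235.
- s = 12/60 = 20%: 0.80 remains. The factor is 1/0.80² = 1.562.

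The loss is smaller if people switch later. For an outcome that accrues over 52 weeks, such as time in remission, a switch at week 26 with an immediate, constant effect counts for (52 − 26)/52 = one half. The remaining share is then 0.95 at 10% and 0.90 at 20%.

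**4. Persistence, under two possible counting rules.** Suppose true persistence P is the same in both arms, and a share s of eMoods persisters switches only because of emailing.

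- *Switchers stay in the eMoods arm and their later entries count.* If they keep up their entries, the false difference is 0.
- *Switchers count as not persisting.* The false difference is P − P(1 − s) = P × s. It runs from 0.7 × 0.05 = 0.035 to 0.9 × 0.20 = 0.18. At P = 0.8 and s = 10% it is 0.80 against 0.72. With 60 per arm, the chance that a two-sided 0.05 test declares this false difference runs from about 6% (P = 0.7, s = 5%) to about 72% (P = 0.9, s = 20%).

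The documents do not choose between these rules, so the second set of figures shows what hangs on the omission and does not predict a bias.

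**The case against.** A reader might infer that the plan burdens the comparator with an optional task foreign to the app and so tilts the trial towards KIOS-Bipolar. The documents do not support that reading, for these reasons:

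- **What is optional.** Only weekly timing is clearly optional. The data must still reach the study by the visit, and no route other than sending is described. The clause may be aimed at participants whose data could not be captured at all.
- **Relation to the app.** Item g of the trial's list of objectives treats submitting displays to the investigative staff as an ancillary feature of either app whose utility is to be estimated. Trouble sending is therefore not wholly outside what is being evaluated.
- **Asymmetry.** Both arms may switch for trouble with the entry itself and under an open-ended technical ground. Only the emailing ground is one-sided, and that is because only eMoods has the step.
- **Direction.** For clinical outcomes analysed as randomized, the crossover pulls the result towards no difference. That works against hypotheses a and e and does not harm eMoods.
- **Persistence.** Hypothesis b defines persistence by weekly completion of the scales and by finishing the 52 weeks. A switcher who carries on could satisfy both. A handicap to eMoods needs a counting rule that the plan does not contain.
- **Satisfaction.** The content of the software evaluation form is not given, so an effect on ratings is possible but not shown. The evaluation sheets already invite notes on obstacles to use.

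All of this stands and limits the point. What remains is the mismatch between the emailing ground and the rule's own condition, and the one-way crossover it permits. If few participants would use the clause, little is lost by removing it.

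**Conclusion.** The point holds in a limited form. Trouble with emailing does not by itself meet the condition for switching, and listing it as a ground permits avoidable crossover from eMoods to KIOS-Bipolar only. If used, it dilutes the as-randomized clinical contrast: 10% to 20% switching leaves about 90% to 80% of the true difference. That rests on assumed switch counts, an assumed 60 per arm, early switching and full effect of the new app; later switching costs less. Effects on persistence and attrition could range from none to material, depending on how switchers and unsent entries are counted. The actual size cannot be derived from the documents. They do not support a conclusion that the comparator is systematically disadvantaged.

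**What to change.** 1. Delete the emailing clause from the switching grounds, and limit switching in both arms to one condition: the participant cannot make the weekly entry in the assigned app. The open-ended technical ground must be brought under this condition too, or it would let emailing trouble back in.
2. State that a participant with emailing trouble stays on eMoods and that entries are collected at the next scheduled visit, from the device if sending fails. This last route is new, since the protocol describes no alternative to sending.
3. Count an eMoods week as completed, and as on time, by the date of entry and not the date of transmission. Confirm beforehand that the app keeps that date; the documents do not say.
4. Analyse any switchers in the arm to which they were randomized, and record the date of and reason for each switch.

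The cost is a few sentences of protocol text, a field for the reason for switching, and some coordinator time at visits. Some eMoods data will reach the study later, which the existing option to postpone sending already accepts.
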